2.3.2 Study design for subjects with erythrodermic PSO or generalized pustular PSO

2.3.2.1 Period 1: Screening

The Screening Period of 2 to 5 weeks will be used to confirm eligibility and obtain laboratory data.

2.3.2.2 Period 2: Initial Period - Week 0 to Week 16

At least 10 subjects in the cohort with erythrodermic PSO or generalized pustular PSO will be allocated in a 1:1 ratio to the following open-label study treatments:

- CZP 400mg (n ≥ 5): CZP administered sc at the dose of CZP 400mg Q2W
- CZP 200mg (n ≥ 5): CZP administered sc at the dose of CZP 400mg at Weeks 0, 2, and 4, followed by CZP 200mg Q2W (starting at Week 6)

2.3.2.3 Period 3: Maintenance Period - Week 16 to Week 52

The treatment received in Period 3 will be based on the initial study treatment and on response to open-label treatment at Week 16:

- Subjects achieving a “much improved” or “very much improved” in the Global Improvement Score (for subjects with generalized pustular PSO) or a PASI50 response (for subjects with erythrodermic PSO) will continue to receive the same treatment as randomized.
- Subjects in the CZP 200mg Q2W group who are not in response (not achieving “much improved” or “very much improved” in the Global Improvement Score [for subjects with generalized pustular PSO] or a PASI50 response [for subjects with erythrodermic PSO]) will be allowed to have their dose increased to CZP 400mg Q2W, at the discretion of the Investigator. Subjects randomized to CZP 400mg Q2W will continue to receive CZP 400mg Q2W at the discretion of the Investigator. If, in the opinion of the Investigator, the subject is not receiving benefit at the 400mg Q2W dose, the subject could be withdrawn from the study. Per the Withdrawal Criteria, subjects who develop an aggravation of the primary disease or concomitant disease with hospitalization in the opinion of the Investigator must be withdrawn from the study.

2.3.2.4 Period 4: Safety Follow-up: Week 52 to Week 60

All subjects, including those withdrawn from study treatment, will have a Safety Follow-Up Visit, 10 weeks after their final dose of study medication.

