3.6.2 Subjects with erythrodermic PSO or generalized pustular PSO

Period 2 – Initial Period - Week 0 to Week 16

Efficacy and Safety Evaluations:

Efficacy and Safety data will be presented by the following randomized treatment groups:

- Erythrodermic PSO CZP 200mg Q2W
- Erythrodermic PSO CZP 400mg Q2W
- Erythrodermic PSO All CZP (only for safety data)
- Generalized Pustular PSO CZP 200mg Q2W
- Generalized Pustular PSO CZP 400mg Q2W
- Generalized Pustular PSO All CZP (only for safety data)
- All Subjects (only for safety data)

Selected parameters (where stated in the following sections) may be summarized by treatment group and subgroup (Definition of subgroups, see [Section 4.8](#)).

Period 3 – Maintenance Period - Week 16 to Week 52

Efficacy Evaluations:

During the 36-week Period 3, subjects will be allocated to dose groups based on their Week 16 PASI50 response/Global Improvement Score, as appropriate based on PSO type, and whether or not the subject ever up-titrated their dose during the Maintenance Period. Efficacy data will be summarized based on the following maintenance treatment groups:

- Erythrodermic PSO CZP 200mg Q2W/CZP 200mg Q2W – includes subjects who remained on CZP 200mg Q2W for the duration of both periods
- Erythrodermic PSO CZP 400mg Q2W/CZP 400mg Q2W – includes subjects who remained on CZP 400mg Q2W for the duration of both periods
- Erythrodermic PSO CZP 200mg Q2W/CZP 400mg Q2W – includes subjects who up-titrated to CZP 400mg Q2W at any point during the Maintenance Period
- Generalized Pustular PSO CZP 200mg Q2W/CZP 200mg Q2W – includes subjects who remained on CZP 200mg Q2W for the duration of both periods

- Generalized Pustular PSO CZP 400mg Q2W/CZP 400mg Q2W – includes subjects who remained on CZP 400mg Q2W for the duration of both periods
- Generalized Pustular PSO CZP 200mg Q2W/CZP 400mg Q2W – includes subjects who up-titrated to CZP 400mg Q2W at any point during the Maintenance Period

Safety Evaluations:

For safety analysis, data of the Combined Initial and Maintenance Period will be summarized using the same treatment groups as listed for the Initial Period. Additionally, all Generalized Pustular PSO, all Erythrodermic PSO and all subjects will be summarized.

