- Date of last administration of open-label study medication – date of first administration of open-label study medication at/after Week 16 + 70 days
- Date of last clinical contact – date of first administration of open-label study medication at/after Week 16 + 1 day

For subjects who die prior to the Week 52 visit: Date of death – date of first administration of open-label study medication at/after Week 16 + 1 day.

For cohort subjects who remain on open-label CZP 400mg Q2W during Maintenance and who complete the Week 52 visit, the following will be attributed to open-label CZP 400mg Q2W:

- Date of Week 50 administration of open-label study medication – date of first administration of open-label study medication at/after Week 16 + 70 days
- If the subject did not receive a dose at Week 50, this algorithm reverts to: Date of last administration of study medication – date of first administration of open-label study medication at/after Week 16 + 70 days.

For cohort subjects who remain on open-label CZP 400mg Q2W during Maintenance and who discontinued prior to Week 52, use the minimum of the following which will be attributed to open-label CZP 400mg Q2W:

- Date of last administration of open-label study medication – date of first administration of open-label study medication at/after Week 16 + 70 days
- Date of last clinical contact – date of first administration of open-label study medication at/after Week 16 + 1 day

For subjects who die prior to the Week 52 visit: Date of death – date of first administration of open-label study medication at/after Week 16 + 1 day.

For plaque PSO subjects who escape to CZP 200mg Q2W at/after Week 16 and subsequently up-titrate to CZP 400mg Q2W, or for cohort subjects who subsequently up-titrate to CZP 400mg Q2W at/after Week 16, time at risk to each open-label dose will be calculated as follows:

- For open-label CZP 200mg Q2W: Date of first administration of open-label CZP 400mg Q2W treatment – date of first administration of open-label CZP 200mg Q2W study medication at/after Week 16.
- For CZP 400mg Q2W, if the subject completed the Week 52 visit:
 - o Date of Week 50 administration of open-label CZP 400mg Q2W – date of first administration of open-label CZP 400mg Q2W at/after Week 16 + 70 days
 - o If the subject did not receive a dose at Week 50, this algorithm reverts to: Date of last administration of open-label CZP 400mg Q2W – date of first administration of open-label CZP 400mg Q2W at/after Week 16 + 70 days.

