For subjects who die, this calculation reverts to date of death – date of first administration of open-label CZP 400mg Q2W study medication + 1 day.

- If the subject was not initially randomized to CZP 200mg Q2W or CZP 400mg Q2W and discontinues prior to the Week 52 visit:
 - Date of Week 16 administration of study medication – date of Week 0 administration of study medication is attributed to the original treatment
 - Date of first administration of open-label CZP 400mg Q2W study medication – date of first administration of open-label CZP 200mg Q2W study medication is attributable to CZP 200mg Q2W.
 - For CZP 400mg Q2W, use the minimum of the following:
 - (1) Date of last administration of open-label CZP 400mg Q2W study medication – date of first administration of open-label CZP 400mg Q2W study medication + 70 days
 - (2) Date of last clinical contact – date of first administration of open-label CZP 400mg Q2W study medication + 1 day

For subjects who die, this calculation reverts to date of death – date of first administration of open-label CZP 400mg Q2W study medication + 1 day.

Combined Initial and Maintenance Period

Cohort subjects

Duration of exposure

For subjects who discontinue on/prior to the Week 16 visit:

- Date of last administration of study medication – date of first administration of study medication + 14 days

For subjects who die, if date of last administration of study medication + 14 days extends to a date beyond the date of death, then this calculation reverts to date of death – date of first administration of study medication + 1 day

For subjects who do not up-titrate to CZP 400mg Q2W at Week 16 or at any point during Maintenance:

- Date of last administration of study medication – date of first administration of study medication + 14 days

For subjects who die, if date of last administration of study medication + 14 days extends to a date beyond the date of death, then this calculation reverts to date of death – date of first administration of study medication + 1 day.

For subjects who do up-titrate to CZP 400mg Q2W during Maintenance:

- Date of first administration of CZP 400mg Q2W study medication – date of first administration of CZP 200mg Q2W study medication is attributable to CZP 200mg Q2W.
- Date of last administration of CZP 400mg Q2W study medication – date of first administration of CZP 400mg Q2W study medication + 14 days is attributable to CZP 400mg Q2W.

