- Date of last administration of study medication – date of first administration of study medication + 14 days is attributable to “All CZP”.

For subjects who die, if date of last administration of study medication + 14 days extends to a date beyond the date of death, then this calculation reverts to date of death – date of first administration of CZP study medication + 1 day.

Number of days a dose was received

For subjects who discontinue on/prior to the Week 16 visit:

- Total number of dose days from Week 0 to last dose received (inclusive).

For subjects who do not up-titrate at Week 16 or at any point during Maintenance:

- Total number of dose days from Week 0 to last dose received (inclusive).

For subjects who do up-titrate to CZP 400mg Q2W during Maintenance:

- Total number of dose days from Week 0 to last dose of CZP 200mg Q2W study medication received (inclusive) is attributable to CZP 200mg Q2W
- Total number of dose days from escape through last dose received is attributable to CZP 400mg Q2W

Patient exposure days at risk

For subjects who discontinue on/prior to the Week 16 visit, use the minimum of the following:

- Date of last administration of study medication – date of first administration of study medication + 70 days
- Date of last clinical contact – date of first administration of study medication + 1 day

For subjects who die, this calculation reverts to date of death – date of first administration of study medication + 1 day

For subjects who do not up-titrate at Week 16 or at any point during Maintenance, and who complete the Week 52 visit:

- Date of Week 50 administration of study medication – date of first administration of study medication + 70 days

- If the subject is missing their Week 50 injection date, then this calculation reverts to:
Date of last administration of study medication – date of first administration of study medication + 70 days.

For subjects who die, this calculation reverts to date of death – date of first administration of study medication + 1 day.

For subjects who do not up-titrate at Week 16 or at any point during Maintenance, and who discontinue prior to the Week 52 visit, use the minimum of the following:

- Date of last administration of study medication – date of first administration of study medication + 70 days
- Date of last clinical contact – date of first administration of study medication + 1 day

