For subjects who die, this calculation reverts to date of death – date of first administration of study medication + 1 day

For subjects who do up-titrate to CZP 400mg Q2W during Maintenance:

- Subjects who complete the Week 52 visit:
 - Date of first administration of open-label CZP 400mg Q2W study medication – date of first administration of open-label CZP 200mg Q2W study medication is attributable to CZP 200mg Q2W.
 - Date of last administration of open-label CZP 400mg Q2W study medication – date of first administration of open-label CZP 200mg Q2W study medication + 70 days is attributable to CZP 400mg Q2W.

For subjects who die, this calculation reverts to date of death – date of first administration of open-label CZP 400mg Q2W study medication + 1 day.

- Subjects who discontinue prior to the Week 52 visit:
 - Date of first administration of open-label CZP 400mg Q2W study medication – date of first administration of open-label CZP 200mg Q2W study medication is attributable to CZP 200mg Q2W.
 - For CZP 400mg Q2W time at risk, use the minimum of the following:
 - (1) Date of last administration of open-label CZP 400mg Q2W study medication – date of first administration of open-label CZP 400mg Q2W study medication + 70 days
 - (2) Date of last clinical contact – date of first administration of open-label CZP 400mg Q2W study medication + 1 day

For subjects who die, this calculation reverts to date of death – date of first administration of open-label CZP 400mg Q2W study medication + 1 day.

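### Two time-at-risk rules in SAP 10.1.2 are wrong as written and distort the final exposure-adjusted adverse event rates

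*SAP*

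**What the plan says.** All rules below are in SAP 10.1.2, Combined Initial and Maintenance Period, unless stated. SAP 10.2 makes the Section 10.1 time-at-risk definitions the denominators of EAIR and EAER.

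**(a) Cohort subjects who up-titrate and complete Week 52.** The 200mg time runs from the first 200mg dose to the first 400mg dose. The 400mg time is the last 400mg dose minus "date of first administration of open-label CZP 200mg Q2W study medication + 70 days is attributable to CZP 400mg Q2W". Three parallel rules start 400mg time at the first 400mg dose:

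- the discontinuer rule just below it: "date of first administration of open-label CZP 400mg Q2W study medication + 70 days";
- the cohort duration rule: "date of first administration of CZP 400mg Q2W study medication + 14 days is attributable to CZP 400mg Q2W";
- the Maintenance Period open-label rule: "date of first administration of open-label CZP 400mg Q2W at/after Week 16 + 70 days".

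The cohort duration rules give up-titrators an All CZP line ("date of first administration of study medication + 14 days is attributable to" All CZP). The cohort time-at-risk rules do not.

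**(b) Plaque subjects switched from 200mg Q2W to 400mg Q4W who complete without escaping (blinded plus open-label).** All CZP time at risk is the Week 50 dose minus the Week 0 dose, with no tail. The same subjects' 400mg Q4W time, their All CZP rule in the blinded-only section, and the All CZP rule for switchers who discontinue all add 70 days. SAP 10.2 counts completers' treatment-emergent events up to 70 days after the Week 50 dose.

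**(c) Deaths among discontinuers.** For three groups, the plaque blinded plus open-label rules add an earlier segment on the same dose to the later one, but the death branch gives only the later segment. The groups are: randomised to 400mg, later escape, then up-titration; switch to 400mg Q4W, then escape without up-titration; and randomised to 400mg, escape at Week 16, then up-titration. The matching completer death branches keep both segments.

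**The concern.** Rule (a) counts the 200mg interval twice, and no parallel rule does so. Which column suffers is itself unclear. SAP 3.6.2 says cohort safety "data of the Combined Initial and Maintenance Period will be summarized using the same treatment groups as listed for the Initial Period", that is, by randomised group. SAP 3.6 says safety follows actual treatment, and SAP 10.2 allocates events to the dose most recently received. If time and events are split by dose, the cohort 400mg denominators are too large and their rates too low. If the randomised columns govern, 400mg is untouched and the excess falls on the 200mg column when the two dose-specific times are summed. An All CZP figure built by summing is inflated too.

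Rule (b) counts events over a 70-day window with no person-time for it, so the All CZP EAER is too high. The All CZP EAIR for a given event moves only through switchers who have not had that event before the tail, because time is cut at first occurrence.

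At stake are the rates for all, serious and special-interest events in the final report. Section 10.1 was rewritten in SAP Amendment 2 to remove inconsistencies of this kind, so the text will be programmed as the specification.

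**Working it through.** **Inputs.** First dose = day 0; Week 6 = 42; Week 16 = 112; Week 24 = 168; Week 32 = 224; Week 50 = 350 (intended last dose, SAP 7). SAP 10.1.1 likewise equates 16 weeks with 112 days and 24 weeks with 168. The tail is 70 days. The plan states no time-at-risk total to reproduce, so each rule is applied literally to a subject dosed on schedule.

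**(a) Cohort up-titrators who complete**

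The SAP does not say whether the first 200mg dose means Week 0 or Week 6. The dose-day rule counts the regimen from Week 0: "Total number of dose days from Week 0 to last dose of CZP 200mg Q2W study medication received (inclusive". SAP 2.3.2.2 describes 400mg loading doses at Weeks 0, 2 and 4, with 200mg from Week 6. Both readings are shown.

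- Parallel rules, 400mg time: 350 − 112 + 70 = 308 (up-titration at Week 16); 350 − 168 + 70 = 252 (Week 24).
- As written, Week 0 reading: 350 − 0 + 70 = 420.
- As written, Week 6 reading: 350 − 42 + 70 = 378.

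| Up-titration | Parallel rules | As written (Week 0) | As written (Week 6) |
|---|---|---|---|
| Week 16 | 308 | 420 (×1.36) | 378 (×1.23) |
| Week 24 | 252 | 420 (×1.67) | 378 (×1.50) |

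Sum of both doses, Week 16 case: 112 + 420 = 532 against 112 + 308 = 420 (Week 0 reading); 70 + 378 = 448 against 70 + 308 = 378 (Week 6 reading).

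Illustrative column effect: assume *m* subjects of one subtype randomised to 400mg plus one Week 16 up-titrator, all completing, with time split by dose.

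- Week 0 reading: (420m + 420)/(420m + 308) = 1260/1148 = 1.098 (m = 2); 1680/1568 = 1.071 (m = 3).
- Week 6 reading: 1218/1148 = 1.061; 1638/1568 = 1.045.

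**(b) All CZP for completing switchers**

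- As written: 350 − 0 = 350.
- Sum of the subject's own parts: 112 + (350 − 112 + 70) = 112 + 308 = 420.
- Shortfall: 70 days per subject.

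Assume 15 to 25 such switchers. The ceiling of 25 is all 50 subjects in the 200mg arm re-randomised 1:1, with none escaping or stopping. Missing time is 15 × 70/365.25 = 2.9 to 25 × 70/365.25 = 4.8 patient-years.

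- 100 CZP subjects completing: 42,000 days (115.0 patient-years). EAER ratio 42,000/40,950 = 1.026 to 42,000/40,250 = 1.043.
- Adding 20 placebo subjects who escape at Week 16, at 308 days each: 48,160 days (131.9 patient-years). EAER ratio 48,160/47,110 = 1.022 to 48,160/46,410 = 1.038.

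**(c) Death on day 300, as an example**

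- Randomised to 400mg, escape Week 16, up-titrate Week 24: 112 + (300 − 168 + 1) = 245, against 133 under the death branch.
- Switch at Week 16, escape Week 24: again 245 against 133.
- Randomised to 400mg, escape Week 24, up-titrate Week 32: 168 + (300 − 224 + 1) = 245, against 77.

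Days dropped: 112 in the first two cases; 168 to 280 in the third (escape at Week 24 to Week 40).

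**The case against.** The wording of (a) and (b) is not in dispute; the case on the other side is about weight and scope.

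- **The effect of (a) may be nil.** It needs a cohort subject who both up-titrates and completes, in a cohort planned at 10 or more and split by subtype and dose. No count is given, and the 400mg column is untouched if SAP 3.6.2 governs. This stands, and it is why the column figures are only illustrative.
- **The Week 6 sums mislead.** Under that reading the first 42 days belong to neither dose. Against the full 420 days, 448 is an excess of 28, not 70. This is true of the total; 448 against 378 measures only the double-counted 200mg interval.
- **The lower range for (b) is the relevant one.** SAP 8 expects most placebo subjects to move to CZP, so 2.2% to 3.8% fits better than 2.6% to 4.3%. Accepted.
- **The missing All CZP time-at-risk line is not peculiar to the cohort.** In the plaque blinded plus open-label rules no escaper has one either, so the 308 days used above for placebo escapers are inferred from their 200mg rule. This is correct, and it widens the fix.
- **In (c), the death clause may be meant to replace only the last segment.** Some duration rules use similar shorthand. That is possible, but the completer death branches write out both segments, which favours the literal reading. The text needs clarifying in either case.

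None of this defends the two lines as written.

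**Conclusion.** Both rules are wrong as written, on the SAP's own parallel rules. The error in (a) is certain in form but unknown in pooled size. Each completing subject up-titrated at Week 16 contributes 1.23 to 1.36 times the intended 400mg time, and later up-titration makes it worse. In a subtype column of three or four subjects, one such subject makes the denominator about 4.5% to 9.8% too large if time is split by dose. The error in (b) makes the plaque All CZP EAER about 2.2% to 3.8% too high under the assumed 15 to 25 switchers, 20 placebo escapers and full completion. Item (c) matters only if such a death occurs.

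These are descriptive safety rates. Efficacy, treatment-emergent event counts and percentages, the dose-specific rates of the switchers in (b), and the blinded-only tables are unaffected. The text should still be corrected: literal programming gives wrong rates, and silent correction by the programmers would be an undocumented departure from the SAP.

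**What to change.** In SAP 10.1.2:

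- **(a)** In the cohort completer rule, start 400mg time at the first open-label 400mg dose. Add All CZP time-at-risk lines for up-titrators: completers, last dose − first dose + 70 days; discontinuers, the smaller of that and last clinical contact − first dose + 1 day; deaths, date of death − first dose + 1 day. Add matching lines for plaque escapers, counted from the first CZP dose. Reconcile SAP 3.6.2 with 3.6 and 10.2 on which column holds up-titrators' 400mg time.
- **(b)** Add the 70 days to the All CZP line for completing switchers in the blinded plus open-label section, as the blinded-only section has it.
- **(c)** Restore the earlier same-dose segment in the three discontinuer death branches.

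Smaller clean-up, with no effect on final adverse event rates:

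- limit blinded-only All CZP duration to subjects randomised to CZP;
- in the duration death rule for placebo subjects who escape at Week 16 and up-titrate, use the first rather than the last 400mg dose;
- do not count the first open-label 200mg dose under both doses for subjects randomised to 400mg;
- count All CZP dose days for Week 16 escapers from the first CZP dose;
- reconcile the 160 days given for 24 weeks in SAP 10.2 (24 × 7 = 168; interim only).

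The cost is a few words per rule, mostly copied from parallel rules, and matching programming. No new data are needed.

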10.2 Adverse events

Definitions and Data Handling Conventions

AEs recorded on the Baseline day will be regarded as ‘treatment emergent’. AEs occurring either before study drug administration (pre-treatment) or more than 70 days after last study drug administration will not be considered to be treatment emergent (TEAE). If a subject dies during the treatment period (timeframe: first study drug administration to last study drug administration +70 days), then the period for TEAEs will end with the death date. If a subject

has a Safety follow-up visit that extends beyond 70 days after the last study drug administration, then the period for TEAEs for that subject will end at the last study drug administration + 70 days.

Non treatment emergent AEs will only be listed separately.

Only AEs occurred at or prior to the visit of Week 24 will be included in the interim analysis.

Adverse events that occur on the Week 16 visit date will be attributed to the initial randomized treatment. The only exception to this definition is for the following types of events:

- Those which code to a HLT of “Injection Site Reactions”
- Those which have been designated as an Injection Reaction on the AE CRF and do not code to an SOC of “Investigations”
- Those which have been identified as a hypersensitivity reaction or an anaphylactic reaction

When any of these events occur on the Week 16 visit date, the AE will be attributed to the treatment received at Week 16.

In general, AEs will be allocated to the treatment group based on the dose most recently received.

The following rules will be applied to impute partial onset dates for AEs:

If the AE onset date is completely unknown, then use the date of first dose in the Initial Period.

If only the year is specified:

If the year of first dose in the Initial Period is the same as the year of onset, then use the date of first dose in the Initial Period.

If the year of first dose in the Initial Period is not the same as the year of onset, then use January 1 of the year of onset.

If only the month and year are specified:

If the month and year of first dose in the Initial Period is the same as the month and year of onset, then use the date of first dose in the Initial Period.

If the month and year of onset is after the month and year of first dose in the Initial Period and prior to the month and year of first dose in the Maintenance Period, then use the 1st of the month.

If the month and year of first dose in the Maintenance Period is the same as the month and year of onset, then use the date of first dose in the Maintenance Period.

If the month and year of onset is after the month and year of first dose in the Maintenance Period, then use the 1st of the month.

If the intensity of an adverse event is unknown, it is considered as severe.

If the relationship to study drug is missing, it is considered as related.

Subject time at risk represents the time a subject was at risk for having an AE. The definitions for subject time at risk (in days) for the Initial Period, Maintenance Period, and Combined Initial and Maintenance Period are outlined in [Section 10.1](#). These definitions will be used for

exposure-adjusted AE summaries. Selected AE summaries will include the exposure adjusted incidence rate (EAIR) with associated 95% confidence interval and the exposure adjusted event rate (EAER).

For EAIR, the numerator will be the total number of subjects experiencing the AE. The denominator will be 100 subject-years; that is, the total summation of individual subject-years at risk up to the first occurrence of the AE for subjects with that AE, and the total subject-years at risk for those subjects not experiencing that AE, divided by 100. EAIRs will be presented with a 95% exact confidence interval based upon the Chi-Square distribution (Ulm, 1990).

For EAERs, the numerator will be the number of AEs including repeat occurrences in individual subjects; the denominator will be 100 subject-years. That is, the total summation of individual subject-years at risk divided by 100. No confidence interval will be computed for EAER.

Presentation Conventions

The frequency of all TEAEs during the study period will be presented by treatment group and period separately by SOC, High Level Term (HLT), and preferred term (PT). The data will be displayed as number of subjects experiencing the AE, percentage of subjects, and number of AEs, sorted by descending frequencies of PTs in the 'All CZP Subjects' column and ordered alphabetically for SOC, HLT and identical frequencies for PTs.

Tables for the Incidence of TEAEs – Overview and Incidence of TEAEs will be generated by TE-ADA status using the following categories:

1. TEAEs starting before 1st anti-CZP antibody positive
2. TEAE starting on or after 1st anti-CZP antibody positive
3. TEAEs for subjects who are always anti-CZP antibody negative

Each event will be classified according to whether it occurred on or after the first + result, or for a subject that remained negative throughout. Summaries will include the number of AEs, number of subjects with AEs and percentage of subjects with AEs, incidence rate with 95% CI, and exposure-adjusted event rate. For these summaries, a subject's associated time at risk will be split into the time before the first positive result, and on or after the first positive result. If a subject has multiple reports of the same AE (ie, those which code to the same PT) emerging both prior to first TE-ADA positive result and after first TE-ADA positive result, both events will be summarized in the table in the appropriate column.

Tables for the incidence of TEAEs will be generated for Combined Initial and Maintenance Period by maximum ADA titers using the following categories:

- Low: maximum ADA titer \leq 1024
- High: maximum ADA titer $>$ 1024
- NA: Since ADA titer for escape subjects is measured only at the time of transition and SFU, AEs emerging after escape transition will be included in "NA".

Since this tabulation covers all subjects assigned to CZP, AEs emerging while on PBO are excluded. Also, in order to include all CZP-treated subjects, subjects in the SS and the CSS will be combined together into a single table.

Finally, AEs of interest (AEOIs) will be evaluated as described below:

- Serious infections, including opportunistic infections. Serious infections will be summarized using the previously described “Any SAE” table. In addition, opportunistic infections (including tuberculosis) will be presented in a table using UCB-defined search criteria.
- Malignancies, including lymphoma. These will be presented in 2 tables using the criteria SMQ = “Malignant or unspecified tumours (SMQ)” and SMQ = “Malignant tumours (SMQ)”, respectively. The SMQ search will include terms in the Scope=Narrow group only. Note that the events include in the “Malignant tumours” table will be a subset of the events included in the “Malignant or unspecified tumours” table.
- Congestive heart failure. These will be manually identified by the study physician from the previously described Any TEAE table. No separate table is planned. In addition, serious cardiovascular events will be presented in a table using UCB-defined search criteria.
- Demyelinating-like disorders. These will be presented in a stand-alone table which is based on the SMQ = “Demyelination”. The SMQ search should include all TEAEs which code to a PT included in Scope=Narrow group within the SMQ. TEAEs which code to a PT included in the Scope=Broad group within the SMQ should be excluded from the search.
- Aplastic anemia, pancytopenia, thrombocytopenia, neutropenia, and leucopenia. These will be presented in a table using the criteria SMQ = “Haematopoietic cytopenias (SMQ)” in the subset of SAEs. The SMQ search will include terms in the Scope=Narrow and Scope=Broad groups.
- Serious bleeding events. These will be presented in a table using the criteria SMQ = “Haemorrhage terms (excl laboratory terms) (SMQ)” in the subset of SAEs.
- Lupus and lupus-like illness. These will be manually identified by the study physician from the previously described Any TEAE table. No separate table is planned.
- Serious skin reactions (eg, Stevens-Johnson Syndrome, toxic epidermal necrosis, and erythema multiforme). These will be manually identified by the study physician from the previously described Any SAE table. No separate table is planned.

The tables for the AEOIs will include the incidence rate with associated 95% confidence interval, and the exposure adjusted event rate.

Will also be summarized:

- Hepatic events. They will be identified using the following 5 SMQs: “Cholestasis and jaundice of hepatic origin (SMQ)”; “Hepatic failure, fibrosis and cirrhosis and other liver damage-related conditions (SMQ)”; “Hepatitis, noninfectious (SMQ)”; “Liver-related investigations, signs and symptoms (SMQ)”; and “Liver-related coagulation and bleeding disturbances (SMQ)”.
- Hypersensitivity reactions and anaphylactic reactions. Hypersensitivity reactions will be identified as TEAEs that emerge on the same day or within one day after a study medication injection reaction was received which code to the following 10 PTs: “Administration site hypersensitivity”; “Documented hypersensitivity to administered product”; “Drug hypersensitivity”; “Hypersensitivity”; “Hypersensitivity vasculitis”; “Infusion site hypersensitivity”; “Injection site hypersensitivity”; “Medical device

hypersensitivity”; “Type II hypersensitivity”; “Type IV hypersensitivity reaction”. Anaphylactic reactions will be identified using UCB-defined search criteria.

- Major Cardiovascular Events (MACEs). They will be identified using the following SMQs: “Central nervous system haemorrhages and cerebrovascular conditions (SMQ)”, which includes the 3 following sub SMQs: “Conditions associated with central nervous system haemorrhages and cerebrovascular accidents (SMQ)”, “Haemorrhagic central nervous system vascular conditions (SMQ)”, “Ischaemic central nervous system vascular conditions (SMQ)” except events coding to PT “Transient ischaemic attack”. All serious TEAEs which code to a PT included in the HLT “Ischaemic coronary artery disorders” except events coding to PT “Chest Pain” or “Chest discomfort” and all serious TEAEs which code to a PT included in any of the following HLTs: “Heart Failures NEC”, “Left Ventricular Failures”, or “Right Ventricular Failures” and which also code to the SOC of “Cardiac Disorders” as Primary SOC will be included.

AE Summaries by Period

All of the presentations described above will be presented for the Initial Period. Subsets of the presentations described above will be presented for the Maintenance Period and for the Combined Initial and Maintenance Period. Details for these summaries are described below.

Initial Period

Summaries for the Initial Period will be presented by randomized treatment group (PBO, CZP 200mg Q2W, CZP 400mg Q2W, All CZP) based on the SS, PsA Set and the CSS. For these summaries, treatment-emergence is defined as follows:

- For subjects who complete the Week 16 visit and continue to the Maintenance Period, all AEs which started on or after the date of first dose of study medication and on or prior to the date of the Week 16 administration of study medication will be considered a TEAE for these summaries. The only exception to this rule is for the following types of events:
 - Those which code to a HLT of “Injection Site Reactions”
 - Those which have been designated as an Injection Reaction on the AE CRF and do not code to an SOC of “Investigations”
 - Those which have been identified as a hypersensitivity reaction or an anaphylactic reaction

When any of these events occur on the date of treatment switch at Week 16, the AE will be attributed to the treatment initiated at Week 16.

- For subjects who discontinue on or prior to the Week 16 visit, all AEs which started on or after the first dose of study medication and on or prior to the date of last administration of study medication + 70 days will be considered a TEAE for the analysis summaries.
- For subjects who die prior to the Week 16 visit, all AEs which started on or after the first dose of study medication and prior to or on the date of death will be considered a TEAE for these summaries.

The following AE summaries will be presented:

- Incidence of TEAEs – Overview
- Incidence of TEAEs by TE-ADA status – Overview
- Incidence of TEAEs by TE-ADA status (Includes EAIR and EAER)

- Incidence of TEAEs (includes EAIR and EAER)
- Incidence of Serious TEAEs (includes EAIR and EAER)
- Incidence of TEAEs Resulting in Permanent Discontinuation of Study Drug
- Incidence of TEAEs leading to death
- Incidence of TEAEs by Maximum Intensity
- Incidence of TEAEs by Maximum Relationship
- Incidence of Serious TEAEs by Maximum Relationship
- Incidence of Non-serious TEAEs by Maximum Relationship
- Incidence of TEAEs on or above Reporting Threshold of 5% (not for CSS)
- Incidence of Non-serious TEAEs on or above Reporting Threshold of 5% (not for CSS)
- Incidence of Non-serious TEAEs on or above Reporting Threshold of 5% by Maximum Relationship (not for CSS)
- All AEOI tables

Maintenance Period

The incidence of TEAEs Overview table (open-label) will be provided by treatment group (CZP 200mg Q2W, CZP 400mg Q2W, All CZP) based on the SS. The following AE summaries will be produced considering just those AEs which emerged during the Maintenance Period while on open-label (escape) treatment using the SS and PsAS:

- Incidence of TEAEs – Overview
- Incidence of TEAEs (includes EAIR and EAER)
- Incidence of Serious TEAEs (includes EAIR and EAER)
- Incidence of TEAEs Resulting in Permanent Discontinuation of Study Drug
- Incidence of TEAEs leading to death
- Incidence of TEAEs by Maximum Intensity
- Incidence of TEAEs by Maximum Relationship
- Incidence of TEAEs on or above Reporting Threshold of 5%

Additionally, a listing of TEAEs emerging while on escape treatment will be produced.

Combined Initial and Maintenance Period

Summaries for the Combined Initial and Maintenance Period will be presented by safety treatment group based on the SS, PsAS, and CSS. For these summaries, treatment-emergence is defined as follows:

- For subjects who complete the Week 24 visit, all AEs which started on or after the date of first dose of study medication and on or prior to the date of the Week 24 administration of study medication will be considered a TEAE for the interim analysis summaries.
